5.7 Duration of Subject Participation

Each subject will participate in the study for approximately 1 year. Participation will include an initial evaluation where the decision to undergo implantation of Baerveldt or ClearPath implant is made and a baseline visit. Following surgery, the patient will be evaluated per study schedule (detailed in **Section 2.0**)

5.8 Duration of Study

The clinical portion of the study will last approximately 1 year for each patient enrolled. Study recruitment is anticipated to occur over the course of 2 years with 1 year follow up for each patient enrolled. Therefore, we anticipate a total study duration of 3 years.

6.0 INCLUSION/EXCLUSION CRITERIA

6.1 Inclusion Criteria

- Men or women with age at screening ≥ 18 years and ≤ 90 years
- Inadequately controlled glaucoma
- Valve-less aqueous shunt as the planned surgical procedure
- Patients with primary glaucomas or pseudoexfoliation, pigmentary and traumatic glaucoma with a previous failed trabeculectomy or other intraocular surgery included.
- Primary tubes included
- Investigators to recruit consecutively all eligible patients from their clinics.
- Superotemporal or inferonasal placement of the tube
- Capable and willing to provide consent

6.2 Exclusion Criteria

- NLP
- Unable/unwilling to provide informed consent
- Unavailable for regular follow up
- Previous cyclodestructive procedure
- Prior scleral buckling procedure or other external impediment to supratemporal drainage device implantation
- Presence of silicone oil
- Vitreous in the anterior chamber sufficient to require a vitrectomy
- Uveitic glaucoma
- Neovascular glaucoma
- Nanophthalmos
- Sturge-Weber syndrome or other conditions associated with elevated episcleral venous pressure
- Procedure combined with other surgery
- Any abnormality other than glaucoma in the study eye that could affect tonometry.

7.0 STUDY SCHEDULE (see Flowchart)

All study procedures are performed as standard of care for the condition.

7.1 Surgical Procedure

The patient will undergo standard superotemporal or inferonasal placement of either a Baerveldt or ClearPath implant, which may include placement of a suture ripcord as per the surgeon's preference. The methods utilized to place the tube will vary based on surgeon preference to enhance the generalizability of the results.

7.2 Post-operative interval visits

The subject will be evaluated at post-operative day 1 (± 1 day), week 1 (± 5 days), week 4 (± 1 week), week 6 (± 1 week), month 3 (± 1 week), month 6 (± 2 weeks), and year 1 (± 1 month) as described in **Section 2.0**. Additional appointments may be made as deemed necessary per standard-of-care. The subject will undergo a standard of care post-operative evaluation including assessment of visual acuity, slit lamp biomicroscopy, and tonometry at each interval visit. Addition of glaucoma medications will be at the surgeon's discretion throughout the post-operative period in addition to standard post-operative eye drops, which includes an antibiotic eye drop, a steroid eye drop, and an antibiotic ointment. Ripcord removal and additional glaucoma surgery will be at the surgeon's discretion throughout the post-operative period.

7.3 Post-operative visit year 1 (± 1 month)

The subject will undergo a standard of care post-operative assessment of visual acuity, slit lamp biomicroscopy, and tonometry. At the year 1 post-operative visit, subjects will also undergo visual field testing, optical coherence tomography, pachymetry, and motility testing. Subjects will also complete self-report questionnaires pertaining to dysesthesia and quality of life.

8.0 SUBJECT MONITORING AND DATA COLLECTION PLAN

Clinically indicated care will be provided to all subjects as required. Descriptive statistics will be applied to safety assessments.

8.1 Statistical Considerations

8.1.1 Analysis Plan

The Intent-To-Treat (ITT) population includes all randomized subjects who had at least one post-op assessment. The primary efficacy analysis will be performed on the ITT population with Last Observation Carried Forward (LOCF). If a subject is deemed to have a failed surgery and undergoes a rescue procedure, the last observation collected prior to the intervention will be used for efficacy analyses at all later timepoints.

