2.0 STUDY FLOW CHART

| | | | Study Day | | | | | |
|---|----------------------------|-----------------------|-------------------------|-------------------------|-------------------------|--------------------------|---------------------------|--------------------------|
| | | | | | | | | |
| | Screening / Baseline visit | Post-Op Day 1 ± 1 day | Post-Op Week 1 ± 5 days | Post-Op Week 4 ± 1 week | Post-Op Week 6 ± 1 week | Post-Op Month 3 ± 1 week | Post-Op Month 6 ± 2 weeks | Post-Op Year 1 ± 1 month |
| Informed Consent | X | | | | | | | |
| Review inclusion and exclusion criteria | X | | | | | | | |
| Visual acuity assessment | X | X | X | X | X | X | X | X |
| Slit-lamp biomicroscopy | X | X | X | X | X | X | X | X |
| Applanation Tonometry | X | X | X | X | X | X | X | X |
| Subjective diplopia | | X | X | X | X | X | X | X |
| Pachymetry | X | | | | | | | X |
| Direct fundus exam | X | | | | | | | X |
| Humphrey visual field | X | | | | | | | X |
| Optical coherence tomography | X | | | | | | | X |
| Self-report dysesthesia scale | X | | | | | | | X |
| Motility history and exam | X | | | | | | | X |
| Quality of life questionnaires | | | | | | | | X |

X procedure performed at the time of clinic visit

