3.0 INTRODUCTION

3.1 Background

Implanting aqueous drainage devices has become an increasingly common surgical treatment for glaucoma. Medicare data between 1995 and 2004 demonstrated a steady increase in the use of these devices.^{1,2} Even with the advent of minimally invasive glaucoma surgery (MIGS), aqueous drainage devices is still a mainstay of treatment for uncontrolled intraocular pressure (IOP).³ Currently, one of the most common aqueous drainage devices used is the Baerveldt implant (Johnson & Johnson, Vision, Jacksonville, Florida) (Figures 1&2).

[figure not shown]

Figure 1. Schematic of the different Baerveldt Implant Models available. On the far most right is the Baerveldt 101-350 model that will be utilized in this study.

[figure not shown]

Figure 2. Depiction of typical Baerveldt implant once positioned and implanted on the eye.
www.towerclockeyecenter.com

The Baerveldt implant is an FDA-approved silicone, non-valved implant. This device comes in 3 variants: a single 250 mm² model and two 350 mm² models (Figures 1&2). For the purposes of this study, we will be focusing on the Model BG-101-350, (Figures 1&2) which will be the only variant of the Baerveldt evaluated in this study. As it is non-valved, it needs early restriction of fluid flow to minimize hypotony while the eye forms a fibrous capsule around the implant. One common way of restricting fluid flow is by ligating or tying off the Baerveldt tube with an absorbable suture that dissolves by post-operative week 4 to 6. For better control of the tube opening and intraocular pressure reduction during the post-operative

period, many surgeons place a suture within the lumen of the implant, called a ripcord, at the time of surgery. This ripcord suture is accessible at the slit lamp in clinic.

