The Ahmed ClearPath is a newly developed non-valved glaucoma drainage device that entered United States markets in late 2019 (New World Medical, Inc., Rancho Cucamonga, CA) (Figure 2). This device comes in two sizes: a 250 mm^2 model (Figure 3A) and a 350 mm^2 model (Figure 3B). We will be focusing on the 350 mm^2 model which will be the only variant of the ClearPath evaluated in this study. There are several features of the ClearPath that are advertised as advantageous compared to the Baerveldt. For instance, the 350 mm^2 model features a posteriorly positioned plate in order to avoid intraocular muscle attachment points upon insertion. It has a flexible, contoured design and anteriorly positioned suture points which are intended to optimize the process of device implantation for the surgeon, though this has not yet been confirmed. As it is non-valved implant, it also requires early restriction for the same reasons mentioned for the Baerveldt. However, the ClearPath device comes packaged with a pre-threaded 4-0 polypropylene ripcord though some surgeons do replace this with sutures of differing materials or size per preference.

[figure not shown]

Figure 3. The Ahmed ClearPath 250 mm^2 (A) and 350 mm^2 (B) (www.newworldmedical.com).

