5.3 Sample Size

Approximately 152 subjects will be enrolled in each treatment group for a total of approximately 304 subjects. This sample size was based on a power analysis aimed at detecting a 2 mmHg difference in IOP between the Baerveldt and ClearPath groups with 80% power, using the mean post-op year 1 Baerveldt IOP of 13.6 ± 5.9 mmHg from the pooled AVB and ABC data.⁴ The results were adjusted for an expected 10% drop out rate at 1 year.

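### LOCF is the primary analysis, with no earliest visit set and no sensitivity analysis planned, so an IOP from day 1 to week 4 can stand in for year 1; the likely effect is small but could not be checked

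*Combined protocol and SAP*

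**What the plan says.** Section 8.1.1 sets the primary method: "The primary efficacy analysis will be performed on the ITT population with Last Observation Carried Forward (LOCF". The ITT population "includes all randomized subjects who had at least one post-op assessment". No earliest visit is set for a value to be carried. After a rescue procedure, "the last observation collected prior to the intervention will be used for efficacy analyses at all later timepoints".

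The row "Applanation Tonometry" in the section 2.0 flow chart is marked at baseline and at all seven post-operative visits: day 1, weeks 1, 4 and 6, months 3 and 6, and year 1. Section 7.2 confirms tonometry at each of them.

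Section 5.3 sizes the trial "using the mean post-op year 1 Baerveldt IOP of 13.6", with SD 5.9 mmHg and 10% dropout by 1 year. No section names the primary timepoint; year 1 is inferred from this sizing.

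On early flow, section 3.1 says of the Baerveldt that "it needs early restriction of fluid flow to minimize hypotony while the eye forms a fibrous capsule around the implant", and describes a common method as "tying off the Baerveldt tube with an absorbable suture that dissolves by post-operative week 4 to 6". Of the ClearPath it says that "it also requires early restriction for the same reasons mentioned for the Baerveldt". Section 7.2 leaves the timing of ripcord removal to the surgeon.

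Section 8.1.4 lists the t test for continuous outcomes and Fisher or chi-square tests for categorical ones. No section gives a missing-data assumption, an alternative missing-data method or a sensitivity analysis.

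**The concern.** LOCF assumes that IOP stays flat after the last visit. The protocol's own account of the surgery gives reason to doubt this for the first weeks, because a reading up to about week 4 may precede tube opening. The t test would then treat that reading as an observed year-1 value.

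Two kinds of harm are possible, each under a condition:

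- **Dilution.** If the device difference is smaller early than at year 1, carried values shrink a true difference. This matters here because section 3.2 hypothesises no difference, and a diluted result would look like support for it.
- **Bias.** If early loss or carried IOP differs by arm, the comparison shifts even when the devices are equal. With equal early loss and equal carried values there is no bias under the null.

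With only one missing-data method planned, the report would not show whether either had happened.

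**Working it through.** **1. The plan's own figure.** Inputs: difference 2 mmHg, SD 5.9, two-sided 0.05, 80% power, 10% dropout (sections 5.3 and 8.1.3).

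n per arm = 2 × [5.9 × (1.960 + 0.842) / 2]² = 136.6, and 136.6 / 0.9 = 151.8, so 152. The stated size reproduces. A t test with 137 completers per arm has 79.8% power, which is the reference below.

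**2. Assumptions for LOCF.** The documents give neither early IOP nor dropout timing, so these are assumed:

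- a fraction f of each arm is last seen by about week 4 and carries a value with mean m and SD 8;
- everyone else, including later dropouts, contributes a year-1-like value with SD 5.9 and mean b, where b = 13.6 in one arm and 15.6 in the other;
- all 152 per arm are analysed.

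Arm mean: M = (1 − f)b + fm. 
Arm variance: V = (1 − f)[5.9² + (b − M)²] + f[8² + (m − M)²]. 
Power comes from the noncentral t distribution.

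**3. One case in full: f = 5% (about 8 of 152), m = 18.**

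- Arm 1: M = 0.95 × 13.6 + 0.05 × 18 = 13.82; V = 37.19
- Arm 2: M = 0.95 × 15.6 + 0.05 × 18 = 15.72; V = 36.54
- Difference 1.90; standard error √[(37.19 + 36.54) / 152] = 0.697; noncentrality 2.73; power 77.6%

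**4. Power over a range, true year-1 difference 2 mmHg, no early device difference.**

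| Early loss, each arm | Difference under LOCF | Power, m = 18 | Power, m = 22 |
|---|---|---|---|
| 2% | 1.96 | 81.4% | 80.5% |
| 3% | 1.94 | 80.2% | 78.8% |
| 5% | 1.90 | 77.6% | 75.4% |

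Some values exceed 79.8% because LOCF counts 152 rather than 137 per arm, and late dropouts are assumed to carry year-1-like values. If the second arm is at 11.6 instead of 15.6, 5% early loss gives 76.7% and 73.7%.

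**5. The same with a 2 mmHg early difference.** Carried means are m and m + 2. The LOCF difference stays at 2.00, and power at 5% early loss is 81.3% (m = 18) and 78.9% (m = 22). Most of the loss in step 4 therefore comes from assuming no early difference.

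**6. No true difference, unequal early loss.** Bias = (f₁ − f₂)(m − 13.6).

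| Early loss | m = 18 | m = 22 |
|---|---|---|
| 3% v 2% | 0.04 mmHg; 5.1% false positives | 0.08 mmHg; 5.2% |
| 5% v 2% | 0.03 × 4.4 = 0.13 mmHg; 5.4% | 0.03 × 8.4 = 0.25 mmHg; 6.5% |

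At m = 13.6 the bias is zero. At m = 10 it reverses: 5% v 2% gives −0.11 mmHg and 5.3%.

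**7. Extremes, for scale only.** With m = 30, 5% early loss gives 66.8% power, and 5% v 2% gives 9.8% false positives. If all of the expected 10% dropout came early, power would be 70.9% (m = 18) or 66.7% (m = 22).

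**The case against.** The strongest reply is that realistic inputs show little harm. At 2% early loss there is no power cost for carried means of 10 to 22, and at 3% at most about one point. Five percent would mean that half of the year's expected dropout has happened by about week 4, although section 6.2 excludes patients unavailable for follow-up. Unequal early loss also needs a cause, yet subjects are masked (section 5.6) and both arms share one visit schedule. The IOP failure criteria in section 3.2 apply only after three months, so that measure does not use early readings. All of this stands and sets the size of the point.

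It is also fair to say that a sensitivity analysis alone, with LOCF left primary, would cure the reporting gap, and that a mixed model has its own assumption. Its power advantage is limited. A simplified three-visit calculation with data missing at random gives it 80-81% at 5% early loss. That is 2 to 6 points above LOCF for carried means of about 10 to 22 with no early device difference, with no real gain at 2%. With a 2 mmHg early difference the gain largely disappears.

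A reader might infer three stronger claims that the documents do not support:

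- **Early IOP is high because the tube is closed.** No IOP course is given. Restriction is meant to limit hypotony, and medications may be added at any time (section 7.2), so the direction is open.
- **LOCF necessarily dilutes the difference.** Step 5 shows that this depends on the early device difference, which is unknown.
- **Power falls to about two thirds, or false positives rise well above 5%.** These need all dropout to come early, very high carried values or a marked imbalance between arms. Nothing in the plan points to any of them.

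**Conclusion.** The concern holds in a limited form. The plan lets a reading from day 1 to week 4 serve as the year-1 value, its own description of the surgery gives reason to doubt that reading, and nothing planned would show whether the result depends on it. That gap does not rest on any assumed IOP.

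The size does. Over the moderate range examined, the effect runs from no power cost to about four points (79.8% to 75.4%), with a bias of at most 0.25 mmHg under the null. These figures assume carried means of 18 to 22 mmHg with SD 8, early loss of 2 to 5%, and year-1-like values for later dropouts; the power figure also assumes no early device difference. The likely effect is small. This is a worthwhile, inexpensive improvement; the sample size is sound and need not change.

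The rule for IOP after a rescue procedure is outside this verdict. It raises a separate estimand question, and no effect of it was calculated here.

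**What to change.** - **Section 8.1.1, missed visits only:** make the primary estimate the year-1 device contrast from a mixed model for repeated measures on observed post-operative IOPs, with baseline IOP, device, visit and device by visit, and an unstructured covariance. This also states year 1 as the primary timepoint.
- **Section 8.1.4:** say that this model replaces the t test for that contrast.
- **Sensitivity analyses:** keep LOCF as one, and add a delta-adjusted (tipping-point) multiple imputation.
- **Rescue rule:** not changed by this point.

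The cost is revised wording, one standard model and a few sensitivity runs. IOP is already scheduled at every visit, so no new data, visits or subjects are needed. The downside is that the model relies on data being missing at random, which the tipping-point analysis tests. The changes should be fixed before outcome data are analysed. Clinical management is not affected.

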8.1.2 Study hypotheses

The analysis will be based on the following null hypothesis: there is no difference in IOP or complication rates in patients who undergo Baerveldt implant vs those who undergo ClearPath implants.

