8.1.3 Sample Size Considerations

With a 2-sided significance level of 0.05, a sample size of 152 in each group would be required to detect a 2 mm difference in IOP with 80% power (accounting for a 10% drop out rate). The total planned enrollment for this pilot study is approximately 304 subjects

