8.1.4 Statistical Methods

Descriptive statistical analysis of patient characteristics across the 2 treatment groups will be performed. Snellen VA measurements will be converted to logMAR equivalents for the purpose of data analysis. Student t test for continuous variables, Fisher exact test, and the χ^2 test, or exact permutation χ^2 test for categorical variables will be utilized. All tests will be 2-sided in accordance with our hypothesis. A P-value of 0.05 will be considered statistically significant.

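### The only stated null joins IOP and complication rates, with no declared primary endpoint, time point or multiplicity rule; read literally, its false-positive rate is about 7–10% for two tests

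*Combined protocol and SAP*

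**What the plan says.** All references are to the combined protocol and SAP.

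- **8.1.2** gives the only null hypothesis: "there is no difference in IOP or complication rates in patients who undergo Baerveldt implant vs those who undergo ClearPath implants". No visit and no specific complication is named.
- **8.1.4** provides t tests for continuous variables; for categorical ones, "Fisher exact test, and the χ^2 test, or exact permutation χ^2 test for categorical variables will be utilized". It adds "All tests will be 2-sided in accordance with our hypothesis" and "A P-value of 0.05 will be considered statistically significant". It mentions neither adjustment nor order of testing.
- **8.1.3** ties its significance level to IOP alone: "With a 2-sided significance level of 0.05, a sample size of 152 in each group would be required". It gives no time point.
- **5.3** bases the size on "detecting a 2 mmHg difference in IOP between the Baerveldt and ClearPath groups with 80% power", using a Year 1 Baerveldt mean and SD (13.6 ± 5.9 mmHg) and 10% dropout at one year.
- **8.1.1** refers to a primary efficacy analysis and gives its population and imputation, but not its variable or visit. Its sentence on rescue procedures says the last earlier value "will be used for efficacy analyses at all later timepoints".
- **8.0** says "Descriptive statistics will be applied to safety assessments".
- **4.0** makes complication rates part of the objective, and **3.2** adds a comparison of failure rates.

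**The concern.** A null of no difference in A or B is false as soon as A or B differs. With an unadjusted 0.05 threshold for every test and no other decision rule, one significant result on either outcome is enough to reject the only hypothesis the plan states. The chance of doing so when the devices are equivalent is then above 5%.

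What is at stake is how a positive result can be read. Section 3.2 wants the trial to guide surgeons' choice of device. A chance difference in one complication, or in IOP at one visit, could be reported as a device difference, and the plan would not show whether that comparison had been fixed in advance as the deciding one. Section 8.0 adds to the uncertainty: a reader cannot tell whether complications are to be tested or only described.

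**Working it through.** **Step 1. Reproduce the plan's sample size.** Inputs from 5.3 and 8.1.3: difference 2 mmHg, SD 5.9 mmHg, two-sided alpha 0.05, power 80%, dropout 10%, equal groups.

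n per group = 2 × SD² × (1.960 + 0.842)² / difference² = 2 × 34.81 × 7.849 / 4 = 136.6, so 137 evaluable.

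Dropout: 136.6 / 0.9 = 151.8, so 152. Rounding to 137 first gives 137 / 0.9 = 152.2, so 153. The stated 152 is reproduced. It is the size for one IOP comparison at 0.05, with nothing set aside for complications.

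**Step 2. False-positive rate for the joint null, two tests.** One IOP test and one complication test, each at two-sided 0.05, rejecting if either is significant.

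- Independent: 1 − 0.95² = 0.0975.
- Upper bound whatever the correlation: 0.05 + 0.05 = 0.10.
- Correlated statistics: 1 − P(|Z1| < 1.96 and |Z2| < 1.96), with (Z1, Z2) bivariate normal.

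| Correlation (assumed) | False-positive rate |
|---|---|
| 0 | 9.75% |
| 0.3 | 9.5% |
| 0.5 | 9.1% |
| 0.7 | 8.3% |
| 0.9 | 7.0% |
| 1 | 5.0% |

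The documents give no correlation between IOP and complications, so the whole range is shown. Each test is taken to have a true level of 5%; Fisher's exact test on a rare complication would run somewhat below that.

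**Step 3. More than two tests.** The plan does not say how many visits or complications will be tested. For illustration only, with k independent tests the rate is 1 − 0.95^k: 14.3% for k = 3 and 22.6% for k = 5.

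**Step 4. Compare the remedies.**

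- *Split alpha, 0.025 each:* 2 × 34.81 × (2.241 + 0.842)² / 4 = 165.4, so 166 evaluable and 166 / 0.9 = 184.4, so 185 per group (370 in total). If the trial keeps 137 evaluable per group, power for IOP falls from 80.1% to 71.4%.
- *One primary test, Year 1 IOP at 0.05:* Step 1 applies unchanged, 152 per group.

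**The case against.** The strongest reply is that the plan never promises a familywise level. The 0.05 in 8.1.3 is the alpha behind the IOP sample size, and the one in 8.1.4 is a per-test threshold. A single Year 1 IOP t test holds its 5% however many complications are also tested, and 5.3 points to Year 1 through both the planning data and the dropout figure. This stands as far as it goes: a reader might infer that the plan breaks a stated overall level, and the documents do not support that. But nothing in 8.1 commits the analysis to that single test. The hypothesis on which 8.1.2 bases the analysis includes complications, and the plan states no rule for rejecting it.

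Two other strong readings also fail.

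- **Section 8.0 as a contradiction.** A reader might take it to say that safety is descriptive only. It does not contain that restriction, and describing safety data does not rule out testing complication rates. Nor does 8.1.4 mention complications by name; it speaks of categorical variables. This is a tension to reconcile, not a direct contradiction.
- **Seven IOP tests.** Tonometry is scheduled at seven post-op visits (section 2.0). If each could decide the result, simulation gives 27%, 23% and 18% at assumed common correlations of 0.3, 0.5 and 0.7, and 31%, 27% and 22% with one independent complication test added. But the 8.1.1 wording on later time points is an imputation rule for rescued subjects; it schedules no test at each visit. Section 3.1 describes flow as deliberately restricted in the first weeks, and 3.2 applies its IOP failure criteria only after three months, so early visits are unlikely deciding tests. LOCF also repeats values across visits, which tends to raise correlation and lower the inflation.

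**Conclusion.** The point holds in a limited form. The plan has one compound null, an unadjusted two-sided 0.05 threshold, and no declared primary endpoint, IOP time point, testing order or multiplicity rule. On the literal reading, where either outcome can reject the null, the false-positive rate is about 7–10% for one IOP and one complication test. That rests on two assumptions: the either-test rule, which the plan implies but does not spell out, and correlations between 0 and 0.9, which the documents do not give. The rate would be higher with more tests, by an amount that cannot be fixed from the plan.

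Year 1 is implied by the sizing but not declared. The sample size is sound for a single IOP comparison. A reader might also infer that the sponsor means to pick the deciding visit or complication after seeing the data; the documents show no such intent, only that the wording does not prevent it. The plan should be corrected, and wording is enough.

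**What to change.** - **8.1.2:** make the primary null no difference between arms in mean IOP at post-op Year 1, and state that this is the single confirmatory test, at two-sided 0.05.
- **8.1.1 and 8.1.3:** name the same variable and visit, so that the primary efficacy analysis and the sample size refer to one test.
- **Secondary outcomes:** list complication rates, failure and IOP at other visits as secondary, and name the complications. Report each as a between-arm difference with a 95% confidence interval. Any p-values should be either Holm-adjusted across the named list or labelled exploratory. Complications need not be barred from testing: section 4.0 makes them part of the objective.
- **8.0 and 8.1.4:** say in both places how complication rates will be handled, and that the 0.05 threshold supports a confirmatory claim for the primary test only.

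The cost is a few sentences in an amendment, best made before any between-arm results are seen. Enrolment stays at 152 per group. The downside is that fewer results can be called statistically significant.
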